10.4. Appendix 4: Contraceptive Guidance and Collection of Pregnancy Information

Definitions:

Woman of Childbearing Potential (WOCBP)

A woman is considered fertile following menarche and until becoming post-menopausal unless permanently sterile (see below).

Women in the following categories are not considered WOCBP

- 1. Premenarchal
- 2. Premenopausal female with 1 of the following:
 - Documented hysterectomy
 - Documented bilateral salpingectomy
 - Documented bilateral oophorectomy

Note: Documentation can come from the site personnel's: review of the participant's medical records, medical examination, or medical history interview.

3. Postmenopausal female

- A postmenopausal state is defined as no menses for 12 months without an alternative medical cause. A high follicle stimulating hormone (FSH) level in the postmenopausal range may be used to confirm a postmenopausal state in women not using hormonal contraception or hormonal replacement therapy (HRT). However, in the absence of 12 months of amenorrhea, a single FSH measurement is insufficient.
- Females on HRT and whose menopausal status is in doubt will be required to use one of the non-estrogen hormonal highly effective contraception methods if they wish to continue their HRT during the study. Otherwise, they must discontinue HRT to allow confirmation of postmenopausal status before study enrollment.

Contraception Guidance:

Female participants

Female participants of childbearing potential are eligible to participate if they agree to use a highly effective method of contraception consistently and correctly as described in Table 2.

Table 2: Highly Effective Contraceptive Methods

Table 2: Highly Effective Contraceptive Methods

Highly Effective Contraceptive Methods That Are User Dependent a

Failure rate of <1% per year when used consistently and correctly.

Combined (estrogen and progestogen containing) hormonal contraception associated with inhibition of ovulation^b

- Oral
- Intravaginal
- Transdermal

Progestogen only hormonal contraception associated with inhibition of ovulation

- Oral
- Injectable

Highly Effective Methods That Are User Independent ^a

Implantable progestogen only hormonal contraception associated with inhibition of ovulation^b

- Intrauterine device (IUD)
- Intrauterine hormone-releasing system (IUS)
- Bilateral tubal occlusion

Vasectomized partner

A vasectomized partner is a highly effective contraception method provided that the partner is the sole male sexual partner of the WOCBP and the absence of sperm has been confirmed. If not, an additional highly effective method of contraception should be used.

Sexual abstinence

Sexual abstinence is considered a highly effective method only if defined as refraining from heterosexual intercourse during the entire period of risk associated with the study intervention. The reliability of sexual abstinence needs to be evaluated in relation to the duration of the study and the preferred and usual lifestyle of the participant.

NOTES:

- a) Typical use failure rates may differ from those when used consistently and correctly. Use should be consistent with local regulations regarding the use of contraceptive methods for participants participating in clinical studies.
- b) Hormonal contraception may be susceptible to interaction with the study intervention, which may reduce the efficacy of the contraceptive method.

Pregnancy Testing:

- WOCBP should only be included after a negative urine pregnancy test.
- Pregnancy testing will be performed whenever a menstrual cycle is missed or when pregnancy is otherwise suspected

Collection of Pregnancy Information:

• The investigator will collect pregnancy information on any female participant who becomes pregnant while participating in this study. Information will be recorded on the appropriate form and submitted to the sponsor within 24 hours of learning of a participant's pregnancy. The participant will be followed to determine the outcome of the pregnancy. The investigator

will collect follow-up information on the participant and the neonate and the information will be forwarded to the sponsor. Generally, follow-up will not be required for longer than 6 to 8 weeks beyond the estimated delivery date. Any termination of pregnancy will be reported, regardless of fetal status (presence or absence of anomalies) or indication for the procedure.

- While pregnancy itself is not considered to be an AE or SAE, any pregnancy complication or elective termination of a pregnancy will be reported as an AE or SAE. A spontaneous abortion is always considered to be an SAE and will be reported as such. Any post-study pregnancy related SAE considered reasonably related to the study intervention by the investigator will be reported to the sponsor as described in Section 8.3.4. While the investigator is not obligated to actively seek this information in former study participants, he or she may learn of an SAE through spontaneous reporting.
- Any female participant who becomes pregnant while participating in the study will be withdrawn from the study.

# **VERSION HISTORY**

Version	Version Date	Description
1.0	13 November 2020	Original signed version
2.0	20 January 2021	Updated dictionary version to MedDRA
	:	v23.0

# LIST OF ABBREVIATIONS

Abbreviation	Definition
ADaM	Analysis Data Model
ANCOVA	Analysis of Covariance
AE	Adverse event
ATC	Anatomical therapeutic chemical
CDISC	Clinical Data Interchange Standards Consortium
CRF	Case report form
CSR	Clinical Study Report
DSMB	Data Safety Monitoring Board
ECG	Electrocardiogram
ICF	Informed consent form
ITT	Intent-to-Treat
IVRS/IWRS	Interactive Voice/Web Response System
MedDRA	Medical Dictionary for Regulatory Activities
MMRM	Mixed-Model Repeated Measures
MoCA	Montreal Cognitive Assessment
MSA	Multiple System Atrophy
MSA-QoL	MSA Health-Related Quality of Life
PD	Protocol Deviation
SAE	Serious adverse event
SAP	Statistical Analysis Plan
SDTM	Study Data Tabulation Model
TEAE	Treatment-emergent adverse event
UDRS	Unified Dystonia Rating Scale
UMSARS	Unified MSA Rating Scale
WHO	World Health Organization

#### 1 INTRODUCTION

The purpose of this Statistical Analysis Plan (SAP) is to provide a description of the statistical methods to be implemented for the analysis of data from the study with protocol number Z7219K01. The SAP will be finalized prior to database lock. Any deviations from the SAP after database lock will be documented in the final Clinical Study Report (CSR).

#### 2 STUDY OVERVIEW

# 2.1 Study Objectives

The primary objective of this study is to evaluate the safety and tolerability of safinamide, 200 mg od, compared with placebo.

The other objective is to evaluate the potential efficacy of safinamide 200 mg od, as add-on therapy, on motor function and/or quality of life.

# 2.2 Study Design

#### 2.2.1 Overview

The overall design is a parallel group, placebo controlled, double blind study.

[figure not shown]
The target population are participants diagnosed, less than two years ago, with possible or probable parkinsonian variant of Multiple System Atrophy (MSA) who are on stable doses of levodopa and/or dopamine agonist, anticholinergic and/or amantadine.

Trial participation will be up to a maximum duration of 14 weeks and will comprise a screening period (up to 2 weeks), a run in period of 2 weeks (week 1 – week 2) during which study participants will receive 1 tablet (either 100 mg safinamide or matching placebo) followed by a treatment period (week 3 – week 12), during which they will receive two tablets (200 mg safinamide or matching placebo) once daily, taken in the morning in addition to their daily levodopa dose (and/or the above mentioned allowed MSA treatments). In the event the study participant does not tolerate 2 tablets, they can drop down to 1 tablet per day and remain in the study at that dose level.

A telephone follow-up call will be performed 2 weeks after the end of treatment. The treatment duration is sufficiently long to evaluate the safety and tolerability of safinamide 200 mg od and potentially show symptomatic efficacy.

A study schema is depicted in Figure 1. The schedule of study assessments is described in Table 1.

# FIGURE 1: SCHEMA

# **TABLE 1: SCHEDULE OF ACTIVITIES**

Study Period	Screening period	Baseline		terim Vi		EOT / ET Week 12	Telephone follow-up Week 14	Notes
Day	-14 to -0	1	14±3	28 ±3	56 ±3	84 ±3	98 ±3	In the event of early termination (ET) participants should complete the End of Treatment (EoT) assessments
Visit	1	2	3*	4*	5*	6*	7	
Informed consent	X							
Eligibility criteria	X	X						
Randomization		X						
Demographics	X							
Medical history/diagnosis	X							
Prior and concomitant medications	X	X	X	X	X	X	X	Details of excluded and permitted concomitant treatments are presented in Section 6.5 of the protocol.
Vital signs	X	X	X	X	X	X		
12-lead ECG	X					X		
Physical & neurological examination	X					X		
UMSARS		X		X	X	X		
MSA-QoL		X		X	X	X		
MoCA	X					X		
UDRS		X		X	Х	Х		To be evaluated at approximately the same time of day as at the baseline visit, and this should be at least 1 hour after the patient has taken their daily dose of safinamide and is in the optimal "ON" state, where possible.
Goniometric assessment		X		X	X	X		

Study Period	Screening period	Baseline		terim Vis Veeks 2 -		EOT / ET Week 12	Telephone follow-up Week 14	Notes
Day	-14 to -0	1	14±3	28 ±3	56 ±3	84 ±3	98 ±3	In the event of early termination (ET) participants should complete the End of Treatment (EoT) assessments
Visit	1	2	3*	4*	5*	6*	7	
Haematology/Clini cal chemistry	X					Х		
Pregnancy test (urine)		X				X		Only for WOCBP.
Adverse events		X	X	X	X	Х	X	
Dispense randomized medication		X	Х	х	X			The first dose of study medication will be administered at the study centre.
Drug accountability			X	X	X	X		

Everything has been documented in the source data as per guidance distributed to the affected sites.

\*= COVID-19 outbreak: in order to ensure the continuity of the study, limiting the subjects' exposure to infection and overcoming travel restriction imposed by governments, sites have been allowed to perform these visits using phone call and/or video – consultation.

#### 2.2.2 Randomization and Blinding

At baseline (Day 1, Visit 2), eligible patients will enter the treatment period (2 titration weeks) and will be randomized to receive either safinamide or matching placebo, orally od in a 2:1 ratio.

IVRS/IWRS	All participants will be centrally assigned to randomized study medication using an Interactive Voice/Web Response System (IVRS/IWRS). Before the study is initiated, the telephone number and call-in directions for the IVRS and/or the log in information & directions for the IWRS will be provided to each site.
	Study medication will be dispensed at the study visits summarized in SoA.
	Returned study medication should not be re-dispensed to the participants.
Blind Break (IVRS/IWRS)	The IVRS/IWRS will be programmed with blind-breaking instructions. In case of an emergency, the investigator has the sole responsibility for determining if unblinding of a participants's treatment assignment is warranted. Participant safety must always be the first consideration in making such a determination. If the investigator decides that unblinding is warranted, the investigator should make every effort to contact the sponsor prior to unblinding a participant's treatment assignment unless this could delay emergency treatment of the participant. If a participant's treatment assignment is unblinded, the sponsor must be notified within 24 hours after breaking the blind. The date and reason that the blind was broken must be recorded in the source documentation and case report form, as applicable.

#### 2.2.3 Sample Size Determination

As this is a pilot study with a focus on evaluating the safety of safinamide, no formal sample size has been calculated. Approximately 56 participants will be screened to achieve 48 randomly assigned (2:1 active vs placebo) to study medication and 40 evaluable participants for an estimated total of respectively 26 and 14 evaluable participants per group.

# 2.3 Study Endpoints

#### 2.3.1 Efficacy Endpoints

Efficacy endpoints include the change from baseline to Weeks 4, 8 and 12 in the following parameters:

- Goniometric measurement for "lateral" and "anterior" displacement
- Unified MSA Rating Scale (UMSARS) Part II
- MSA Health-Related Quality of Life (MSA-QoL) scale

- Montreal Cognitive Assessment (MoCA) scale (Week 12 only)
- Unified Dystonia Rating Scale (UDRS)

#### 2.3.1.1 Goniometric measurement

Goniometric measurement of "lateral" and "anterior" displacement is determined using a wall goniometer and expressing the value in degrees in the range of 0-90.

#### 2.3.1.2 UMSARS

The Unified MSA Rating Scale (UMSARS) consists of four parts:

- Part I Historical Review has 12 questions rated from 0 to 4, giving a range of 0-48 in the total score. Higher values indicate worse functional situation.
- Part II Motor Examination Scale has 14 questions rated from 0 to 4, giving a range of 0-56 in the total score. Higher values indicate worse functional situation.
- Part III Autonomic Examination has assessments of systolic blood pressure, diastolic blood pressure, heart rate and orthostatic symptoms (yes/no). Blood pressure and heart rate are measured after 2 minutes of rest and again after 2 minutes of standing.
- Part IV Global Disability Scale ranges from 1 to 5 (1=completely independent; 2=not completely independent; 3=more dependent; 4=very dependent; 5=totally dependent and helpless).

#### 2.3.1.3 MSA-QoL

The MSA Health-Related Quality of Life (MSA-QoL) scale has 40 questions on an ordinal scale of "no problem", "slight problem", "moderate problem", "marked problem", and "extreme problem". Additionally, patients were asked to indicate life satisfaction at the moment on a scale of 0 (extremely dissatisfied) to 100 (extremely satisfied).

#### 2.3.1.4 MoCA

A score ranging from 0 to 30 will be recorded for each patient according to the Montreal Cognitive Assessment (MoCA) scale. Higher scores indicate better cognitive function.

#### 2.3.1.5 UDRS

The Unified Dystonia Rating Scale (UDRS) assesses the severity and duration of dystonia in individual body areas. Each of 14 body area is evaluated via a 5-point ordinal scale of severity (0=none; 1=mild; 2=moderate; 3=severe; 4=extreme) and duration (0=none; 0.5=occasional, predominantly submaximal; 1.0= occasional, predominantly maximal; 1.5= intermittent, predominantly submaximal; 2.0= intermittent, predominantly maximal; 2.5= frequent, predominantly submaximal; 3.0= frequent, predominantly maximal; 3.5= constant, predominantly submaximal; 4.0=constant, predominantly maximal). A total score will be calculated as the sum of the severity and duration factors. If any of the factors is missing, then the total score is considered as missing. The total score ranges from 0 to 112.

# 2.3.2 Safety Endpoints

Safety endpoints include the following parameters:

- The nature, frequency, severity, relationship (to study drug), actions taken, and outcome of TEAEs and SAEs.
  - Adverse events will be coded using Medical Dictionary for Regulatory Activities (MedDRA) Version 23.0. The severity of AEs will be assessed using "mild", "moderate" and "severe". The degree of "relatedness" of the AE to the study treatment will be described using "related to study drug" and "not related to study drug".
  - Treatment-emergent adverse events (TEAEs) are defined as those AEs that have a start date on or after the first administration of study drug. AEs with unknown/unreported onset date will also be counted as TEAE.
- Physical and neurological examination findings.
  - Physical and neurological examinations will be performed at Screening and Week 12. Results will be recorded as "abnormal", "normal" and "not assessed".
- Vital sign (heart rate, systolic and diastolic blood pressure) values.
  - o Vital signs will be assessed at Screening, Day 1, 14, 28, 56, and Day 84/Week 12.
- 12-lead Electrocardiogram (ECG) parameter measures.
  - o 12-lead ECG will be performed at Screening and Week 12.
- Clinical chemistry and hematology values.
  - Clinical chemistry and haematology evaluations will be performed at Screening and Week 12.
- Number of withdrawals (and reason if given).
  - O Subject withdrawals from the study will be recorded on the End of Study CRF with reasons provided.

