Multiple System Atrophy (MSA) is a progressive and fatal neurodegenerative disease. MSA is characterized pathologically by glial cytoplasmic inclusions (GCIs) that consist of ectopic aggregates of hyperphosphorylated and insoluble filamentous α-synuclein in oligodendrocytes (Tu PH, 1998) and selective neurodegeneration in the striatonigral and olivopontocerebellar regions. Microglial activation parallels the neurodegeneration and GCI pathology in MSA (Ishizawa K, 2004).

Clinically, the cardinal features include autonomic failure, parkinsonism, cerebellar ataxia, and pyramidal signs in any combination. Two major motor presentations can be distinguished clinically. Parkinsonian features predominate in 80% of patients (MSA-P subtype), whereas cerebellar ataxia predominates in the remaining 20% of patients (MSA-C subtype). MSA is a progressive disorder with early disability and shortened life expectancy.

No cures are available and treatment is symptomatic. Levodopa is used to manage the motor symptoms, but patients become rapidly irresponsive to this drug due to widespread glial and neuronal cell degeneration and shrinkage of some brain areas such as cerebellum, basal ganglia and brainstem with eventual death within 9-10 years after diagnosis. Pain is a common non-motor symptom both in PD and MSA (Kass-Iliyya, 2015).

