MSA is a severe neurodegenerative disease for which there are limitations in existing therapy. There is a scientific rationale to assess the clinical benefit of safinamide in MSA patients in this proof of concept study. The existing clinical data on safinamide derived from post marketing surveillance, and clinical studies support an overall, favorable benefit/risk profile. More detailed information about the known and expected benefits and risks as well as reasonably expected adverse events of safinamide may be found in the Investigator's Brochure.

3. Objectives and Endpoints

Objectives	Endpoints
Safety	
To evaluate the safety and tolerability of safinamide, 200 mg od, compared with placebo	 The nature, frequency, severity, relationship (to study drug), actions taken, and outcome of TEAEs and SAEs. Changes in physical and neurological examination findings. Changes in vital sign (heart rate, systolic and diastolic blood pressure) values, including occurrence of abnormalities. Changes in 12-lead ECG parameter measures, including occurrence of abnormalities. Changes in clinical chemistry and hematology values, including shifts from Baseline and occurrence of abnormalities. Number of withdrawals (and reason if given).
Efficacy	
To evaluate the potential efficacy of safinamide 200 mg od, as add-on therapy, on motor function and/or quality of life	 The change from baseline to week 12 in the goniometric measurement for "lateral" and "anterior" displacement Change from baseline at week 12 in Unified MSA Rating Scale, MSA Health-Related Quality of Life (MSA-QoL) scale, Montreal Cognitive Assessment (MoCA) scale, Unified Dystonia Rating Scale (UDRS).

4. Study Design

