5.1. Inclusion Criteria

Participants are eligible to be included in the study only if all of the following criteria apply:

Age

1. Participant must be 30 to 80 years of age inclusive, at the time of signing the informed consent.

Type of Participant and Disease Characteristics

- 2. Participants who are diagnosed with possible or probable parkinsonian variant of Multiple System Atrophy less than 2 years ago (calendar years), with MRI consistent with the diagnosis of MSA and not suggesting an alternative explanation to the clinical diagnosis of MSA (ie it should not have lesions that would suggest an alternative explanation for the symptoms that have been diagnosed as MSA such as subcortical infarctions, neoplasms, etc.)
- 3. Participants with an anticipated survival of at least 3 years in the opinion of the investigator.

Sex

- 4. Male or female
- A female participant is eligible to participate if she is not pregnant, not breastfeeding, and at least one of the following conditions applies (see Appendix 4):
 - i. Not a woman of childbearing potential (WOCBP)

OR

ii. A WOCBP who agrees to follow the contraceptive guidance during the treatment period and for at least 30 days after the last dose of study intervention.

Informed Consent

5. Capable of giving signed informed consent as described in Appendix 1 which includes compliance with the requirements and restrictions listed in the informed consent form (ICF) and in this protocol.

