9.4.1.2. Physical and Neurological Examinations

Physical exam findings will be summarized at baseline and at week 12 in terms of number and proportion of participants with normal/abnormal results per body system and treatment group. Shift tables from baseline to week 12 will be presented.

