#### 3.5.5 Physical and Neurological Examinations

General physical examination and neurological examination results will be listed and summarized by counts and percentages for each treatment group at each scheduled visit.

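### The plan records neurological examination as abnormal, normal or not assessed with no change summary, so worsening of an already abnormal sign cannot show in a safety endpoint defined as change

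*SAP*

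**What the plan says.** Protocol section 3 lists among the safety endpoints: "Changes in physical and neurological examination findings". Protocol 9.4.1 names safety and tolerability as the primary objective. Protocol 9.4.1.2, headed for both examinations but worded for physical findings, planned the "number and proportion of participants with normal/abnormal results per body system and treatment group", with shift tables from baseline to Week 12.

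The SAP (version 2.0; version 1.0 has the same text on this point) handles the endpoint as follows:

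- **Timing (2.3.2):** "Physical and neurological examinations will be performed at Screening and Week 12".
- **Record (2.3.2):** "Results will be recorded as 'abnormal', 'normal' and 'not assessed".
- **Analysis (3.5.5):** "General physical examination and neurological examination results will be listed and summarized by counts and percentages for each treatment group at each scheduled visit".
- **Change from the protocol (5):** shift tables are dropped for all safety assessments, on the ground that abnormal findings will be picked up as AEs.

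Protocol Appendix 3 excludes from the AEs the disease under study and its expected signs, symptoms and progression, unless they are more severe than expected for that participant. Inclusion criterion 2 admits only people with a diagnosis of possible or probable parkinsonian-variant MSA.

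**The concern.** The endpoint is change, but the record is a category without a grade and the analysis is a count at each visit. Everyone enters with a disease whose features are neurological signs, so part or all of the examination is already abnormal before dosing. A sign that gets worse keeps the same label.

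The route offered in place of the shift tables has a gap at the same point. Worsening that the investigator judges to be expected MSA need not be reported as an AE, so it can be absent from both the examination table and the AE tables. This is where a randomised comparison is most useful, because drug effect and disease can look alike. Protocol 8.4 lists postural hypotension among the possible effects of excessive MAO-B inhibition, and the protocol's Introduction names autonomic failure as a cardinal feature of MSA.

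At stake is the reading of a primary-objective endpoint. A flat table could be taken as evidence of no neurological change at 200 mg when the table could not have shown worsening.

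**Working it through.** The documents give no expected share abnormal, no hypothesis and no power for this endpoint, so there is no figure of the plan's own to reproduce. The check has three steps.

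**Inputs.** The recording scale and visits come from SAP 2.3.2. The numbers per arm are 26 and 14 evaluable (Protocol 9.2, SAP 2.2.3), or 48 × 2/3 = 32 and 48 × 1/3 = 16 if all 48 planned randomised participants are examined. The share abnormal at Screening, p, is an assumption and is shown over a range.

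**Step 1: worsening of an existing sign.** The item is abnormal at Screening and abnormal at Week 12. The recorded category does not move. The number of such events visible in the table is 0 for every value of p. This result needs no assumption about saturation.

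**Step 2: a new sign.** It is visible only if the recorded item was normal at Screening. Participants able to show a normal-to-abnormal move = n × (1 − p). For example, 26 × (1 − 0.95) = 1.3 and 14 × (1 − 0.95) = 0.7.

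| Assumed share abnormal at Screening | Of 26 / 14 evaluable | Of 32 / 16 randomised |
|---|---|---|
| 100% | 0 / 0 | 0 / 0 |
| 95% | 1.3 / 0.7 | 1.6 / 0.8 |
| 90% | 2.6 / 1.4 | 3.2 / 1.6 |
| 50% | 13 / 7 | 16 / 8 |
| 30% | 18.2 / 9.8 | 22.4 / 11.2 |

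The upper rows are what one would expect of a single overall result in people who all have parkinsonian-variant MSA. The lower rows could apply to separate items, since the protocol's Introduction says that "the cardinal features include autonomic failure, parkinsonism, cerebellar ataxia, and pyramidal signs in any combination". The documents do not say which form the record takes.

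**Step 3: the AE route.** SAP 5 relies on abnormal findings being captured as AEs. Appendix 3 sorts worsened signs three ways:

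- More severe than expected for that participant: can be an AE.
- Exacerbation of another pre-existing condition, or a newly detected condition: an AE.
- Expected sign or progression of MSA: not an AE.

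The third class reaches neither the AE tables nor, by Step 1, the examination counts when the sign was already abnormal. The premise in SAP 5 therefore does not hold for neurological findings in this population.

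**The case against.** The strongest reply has three parts.

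**Saturation is not documented.** A reader might infer that every participant is abnormal at both visits in both arms, that the largest detectable increase is therefore 0 percentage points, that no new sign can ever appear, and that a shift table would be useless. The documents do not support this. They give no share abnormal. They do not say that the neurological examination has one overall result, and Protocol 9.4.1.2 planned results by body system. The Introduction allows the features in any combination, so some items may be normal at Screening. With item-level recording, a new sign would appear in the counts, in the listing and in a shift table. There is also the third category, not assessed, and Visit 6 could be held by phone or video under the COVID-19 provisions (Protocol 1.3 and 8), so abnormal at both visits is not assured. This part of the reply stands, and it makes the statement about new signs conditional. It does not affect Step 1. For the physical examination, Protocol 8.1.1 lists the nervous system as one entry, so a body-system table would help little in that row.

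**Other measures are graded.** UMSARS Part II has 14 motor items scored 0 to 4. Parts I and II are compared by arm with a repeated-measures model, and Parts III and IV are summarised. UDRS grades dystonia in 14 body areas and is modelled in the same way. This stands in part: motor worsening would probably be noticed there. But these are efficacy measures analysed as totals in the ITT Population (SAP 3.4), and they do not deliver the stated safety endpoint in the Safety Population.

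**AEs still catch serious worsening, and safety is descriptive only.** This is true for worsening beyond what is expected, and SAP 3.5 repeats that abnormal safety assessments will be reported as AEs. That sentence has the same conflict with Appendix 3 as SAP 5. The absence of a hypothesis test does not remove the need for a table that can show change.

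**Conclusion.** The point holds in a limited form. For an endpoint defined as change, the plan has no grade, no change category and no change summary, and its stated substitute is incomplete under the protocol's own AE definition.

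- **Certain from the text:** worsening within an already abnormal item is invisible in the SAP 3.5.5 counts, whatever the baseline share. It may also be absent from the AE tables when judged expected for MSA.
- **Conditional:** if there is one overall neurological result, new signs are largely invisible too. At an assumed 90% to 100% abnormal at Screening, between 2.6 / 1.4 and 0 / 0 of the 26 / 14 evaluable participants could show one. For separate items often normal at Screening the loss is much smaller.
- **Mitigation:** UMSARS and UDRS cover part of the loss, as efficacy measures.

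This should be corrected because it touches the primary objective and costs little. It does not undermine the rest of the safety analysis.

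**What to change.** 1. State in SAP 2.3.2 which neurological items are recorded. At Week 12 or early termination, record change from Screening for each item, and for the nervous-system item of the physical examination, as unchanged, improved, worsened, new or not assessed.
2. In SAP 3.5.5, tabulate by arm, in the Safety Population, the number of participants with at least one new or worsened finding.
3. Reconcile SAP 5 (and the matching sentence in SAP 3.5) with the AE exclusion in Protocol Appendix 3, so that the reason for dropping shift tables is not one that the protocol contradicts.
4. If the case report form can no longer change, and descriptive findings were recorded, derive the same categories by blinded medical review before unblinding. The documents do not state that such descriptions exist. If they do not, restore the per-item shift table and say plainly that worsening within an abnormal item cannot be assessed.

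Cost: one form item or one blinded review, and one table. No new visit or procedure is needed.
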